## **4 Sample Size**

Sample size: 40 subjects (number of subjects started on OPC-61815). For a sample size of 40 subjects, the probability of AE occurring at an incidence of 5% and 4% is respectively 87% and 80%.

## **5 Statistical Analysis Datasets**

### **5.1 Safety Analysis Set**

The safety dataset includes all subjects who received at least one dose of IMP.

### **5.2 Pharmacodynamic Analysis Set**

The pharmacodynamic dataset includes all subjects who received at least one dose of IMP and have postdose pharmacodynamic data.

### **5.3 Efficacy Analysis Set**

The efficacy dataset includes all subjects who received at least one dose of IMP and have postdose efficacy data.

### **5.4 Handling of Missing Data**

Missing data at the time of final IMP administration will be imputed using the last available data obtained by the day after the final IMP administration.

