7.3 Handling of Missing Data

Missing data at the time of final IMP administration will be imputed using the last available data obtained by the day after the final IMP administration.

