Body weight	Before IMP administration on Day 1 (Screening values will be used if the values at screening are measured on Day 1 but not measured prior to the IMP administration on that day.)	Day after final IMP administration
Congestive symptoms (lower limb edema, jugular venous distension, hepatomegaly, pulmonary rales, cardiac third sound)	Screening	Day after final IMP administration
Pulmonary congestion, cardiothoracic ratio	Screening	Day after final IMP administration
Respiratory rate, paroxysmal nocturnal dyspnea, orthopnea	Screening	Day after final IMP administration
Subject-assessed dyspnea	Screening	Day after final IMP administration
NYHA classification	Screening	Day after final IMP administration

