#### 8.3.2.2 Jugular Venous Distension, Hepatomegaly and Cardiothoracic Ratio

Descriptive statistics and two-sided 95% confidence intervals (based on t-distribution) will be calculated for measured values and changes from baseline at the time of final IMP administration. Descriptive statistics will also be calculated at each time point after IMP administration. Note that the absence of jugular venous distension and hepatomegaly will be indicated as 0 cm. The above data on jugular venous distension and hepatomegaly will also be summarized in the same manner for subjects with baseline value. For the presence of jugular venous distension and hepatomegaly, shift tables in changes from baseline at

the final IMP administration and at each time point following IMP administration will be prepared.

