### **9.3 Clinical Laboratory Data**

Clinical laboratory data obtained from central measurements will be used for analyses. For clinical laboratory test parameters other than qualitative urinalysis, measured values and changes from baseline at each time point and at the time of final IMP administration will be summarized using descriptive statistics. For qualitative urinalysis parameters, shift tables will be prepared at each time point and at the time of final IMP administration compared with baseline. In addition, measured values of clinical laboratory test parameters other than qualitative urinalysis will be categorized as below, within, or above the normal range, and shift tables will be prepared at each postdose time point and at the time of final IMP administration compared with baseline.

The numbers and percentages of subjects who have a visit with serum total bilirubin value of  $\geq 2$  times the upper limit of normal (ULN), and an aspartate aminotransferase (AST) or alanine aminotransferase (ALT) value of  $\geq 3$  times the ULN at any postdose time point will be calculated.

The numbers and percentages of subjects experiencing the following events after IMP administration will be calculated.

- A serum sodium concentration  $>147$  mEq/L
- A  $>10$  mEq/L increase in serum sodium concentration within 24 hours after the start of IMP administration

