### **11.3 Biomarkers (Plasma AVP Concentration, Plasma Renin Activity, Plasma BNP Concentration, Serum NT-proBNP Concentration, and Serum Troponin I Concentration)**

Descriptive statistics will be calculated for measured values and changes from baseline at each time point and at the time of final IMP administration.

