CT-6.7 Confidence Interval for Change from Baseline in Cardiothoracic Ratio at the time of Day After Final IMP Administration (Efficacy Analysis Set)

CT-6.8.1 Descriptive Statistics for Jugular Venous Distension (cm) (Efficacy Analysis Set)

CT-6.8.2 Descriptive Statistics for Jugular Venous Distension (cm) (Subjects With Baseline Value in Efficacy Analysis Set)

CT-6.9.1 Descriptive Statistics for Hepatomegaly (cm) (Efficacy Analysis Set)

CT-6.9.2 Descriptive Statistics for Hepatomegaly (cm) (Subjects With Baseline Value in Efficacy Analysis Set)

CT-6.10 Descriptive Statistics for Cardiothoracic Ratio (%) (Efficacy Analysis Set)

CT-6.11 Shift Table for Jugular Venous Distension (Efficacy Analysis Set)

CT-6.12 Shift Table for Hepatomegaly (Efficacy Analysis Set)

CT-6.13 Disappearance Rate for Pulmonary rales and Third Cardiac Sound at the time of final IMP administration (Efficacy Analysis Set)

CT-6.14 Shift Table for Pulmonary rales (Efficacy Analysis Set)

CT-6.15 Shift Table for Third Cardiac Sound (Efficacy Analysis Set)

CT-6.16 Confidence Interval for Change from Baseline in Respiratory Rate (breaths/min) at the time of Day After Final IMP Administration (Efficacy Analysis Set)

CT-6.17 Descriptive Statistics for Respiratory Rate (breaths/min) (Efficacy Analysis Set)

CT-6.18 Disappearance Rate for Paroxysmal Nocturnal Dyspnea and Orthopnea at the time of final IMP administration (Efficacy Analysis Set)

CT-6.19 Shift Table for Orthopnea (Efficacy Analysis Set)

CT-6.20 Shift Table for Paroxysmal Nocturnal Dyspnea (Efficacy Analysis Set)

CT-6.21 Improvement Rate for Subject-assessed Dyspnea at the time of final IMP administration (Efficacy Analysis Set)

CT-6.22 Frequency Distribution for Subject-assessed Dyspnea (Efficacy Analysis Set)

CT-6.23 Improvement Rate for NYHA Classification at the time of Day After Final IMP Administration (Efficacy Analysis Set)

CT-6.24 Shift Table for NYHA Classification (Efficacy Analysis Set)

CT-7.1.1 Extent of Exposure to Investigational Medicinal Product (Safety Analysis Set)

CT-7.1.2 Extent of Exposure to Investigational Medicinal Product by Dose (Safety Analysis Set)

CT-7.1.3 Extent of Exposure to Investigational Medicinal Product Cross Table by Dose, Days (Safety Analysis Set)

CT-7.2.1 Treatment Compliance (Efficacy Analysis Set)

CT-7.2.2 Treatment Compliance (Safety Analysis Set)

CT-8.1 Overall Summary of Adverse Events (Safety Analysis Set)

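### The final-time-point imputation rule has no postdose limit, so a missing end-of-treatment laboratory value (other than sodium or potassium) or biomarker value would, read literally, normally be filled with the Day 1 baseline

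*SAP*

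**What the plan says.** - **The rule.** SAP 5.4: "Missing data at the time of final IMP administration will be imputed using the last available data obtained by the day after" the final dose. Protocol 7.3 agrees: "Missing data at the time of final IMP administration will be imputed using the last available data", with the same cut-off. Neither says that the carried value must be postdose.
- **Where it is used.** For laboratory parameters other than qualitative urinalysis, SAP 9.3 plans descriptive summaries of change at the final time point, and "shift tables will be prepared at each postdose time point and at the time of final IMP administration compared with baseline". SAP 11.3 summarises biomarkers as "measured values and changes from baseline at each time point and at the time of final IMP administration". For the cardiothoracic ratio, SAP 8.3.2.2 plans descriptive statistics and t-based 95% confidence intervals that "will be calculated for measured values and changes from baseline at the time of final IMP" administration, reported in the table "CT-6.7 Confidence Interval for Change from Baseline in Cardiothoracic Ratio at the time of Day After Final IMP Administration".
- **Time points.** SAP Table 3.4-1 sets baseline for laboratory values and biomarkers at predose on Day 1, and for the row "Pulmonary congestion, cardiothoracic ratio" at screening. For all of these the final time point is the day after the last dose.
- **Who is included.** SAP 5.1: "The safety dataset includes all subjects who received at least one dose of IMP". The pharmacodynamic set (SAP 5.2) requires some postdose pharmacodynamic data, but not data on the biomarker being summarised.

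**The concern.** A last-value rule with an upper limit only is harmless where a variable is measured repeatedly on treatment. Where it is measured once before treatment and once at the end, the only value left to carry is the pre-treatment one. A subject with no end-of-treatment sample then appears in the final-time-point tables as having an end-of-treatment result identical to baseline. In a trial whose objective is tolerability, that entry errs towards no change. The analysis sets would not remove such a subject: one dose admits a subject to the laboratory tables, and a postdose urine volume is enough for the biomarker tables.

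**Working it through.** **Plan's own figures.** The documents give no missing-data rate. Their only computed design figure is the chance of seeing at least one adverse event in 40 subjects: 1 − 0.95^40 = 87.1% and 1 − 0.96^40 = 80.5%. These reproduce the stated 87% and 80% and have no bearing on this point.

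**Step 1: which values can be carried?** Schedule from protocol 3.7.1.1 to 3.7.1.7; baselines from SAP Table 3.4-1.

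| Variable | Scheduled before the Day 6/withdrawal assessment | Baseline | Scheduled postdose value to carry? |
|---|---|---|---|
| Central laboratory panel except Na/K | Day 1 predose | Day 1 predose | None |
| Five biomarkers | Day 1 predose | Day 1 predose | None |
| Serum Na, K | Day 1 predose, 4 h and 8 h; predose Days 2 to 5 | Day 1 predose | Yes |
| Cardiothoracic ratio, pulmonary congestion | Screening film; Day 1 predose film unless the screening film was taken that day | Screening | None |
| NYHA class | Screening | Screening | None |

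The lists for Days 2 to 5 (protocol 3.7.1.3, 3.7.1.4, 3.7.1.6) contain no laboratory panel, biomarker, chest film or NYHA assessment. Follow-up laboratory tests come 7 to 10 days after the last dose, past the cut-off. Local screening tests are not candidates, because SAP 9.3 analyses central data. ECG, vital signs and body weight have postdose values and are not normally affected.

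There are two exceptions. A withdrawal assessment done postdose on the last dosing day supplies a postdose value; protocol 3.7.1.7 asks for the following day only where possible. An unscheduled central value could also serve, if the exclusion of unscheduled values in SAP 3.4 is read as covering by-visit summaries only.

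**Step 2: laboratory tests and biomarkers.** The carried value equals baseline, so each of m missing subjects contributes a change of 0:

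reported mean change = observed mean change × (40 − m)/40

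| m (assumed) | Shrinkage, m/40 |
|---|---|
| 0 | 0% |
| 1 | 2.5% |
| 2 | 5% |
| 4 | 10% |

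Each laboratory parameter with a shift table also gains m unsupported no-shift entries.

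**Step 3: cardiothoracic ratio, illustration only.** Assume an observed mean change of −2.0 points, SD 3.0, and a carried value equal to screening. Neither figure is in the documents. With k = 40 − m observed:

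- imputed mean = −2.0 × k/40
- imputed SD = √{[(k − 1) × 9 + (k × m/40) × 4]/39}

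| m | As written (n = 40) | Observed only |
|---|---|---|
| 0 | no effect | no effect |
| 2 | −1.90 (−2.85 to −0.95), SD 2.955 | −2.00 (−2.99 to −1.01), n = 38 |
| 4 | −1.80 (−2.73 to −0.87), SD 2.906 | −2.00 (−3.02 to −0.98), n = 36 |

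At m = 4 the half-widths are 0.929 and 1.015, a ratio of 0.916, so the interval is about 8% narrower than the observed data support. For assumed means of −1 and −3 the ratios are 0.901 and 0.940. If a separate Day 1 predose film exists, a pre-treatment change is instead reported as an end-of-treatment change.

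**Step 4: response rates.** Carrying the screening NYHA class already counts the subject as not improved. The same holds for pulmonary congestion unless a predose Day 1 film differs from screening, and SAP 8.3.2.1 requires the improvement to follow dosing. With an assumed 24 improved of 40, the rate is 60.0% under the current rule and under the fix proposed below.

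**The case against.** **Postdose values were probably intended.** This is possible: several endpoint definitions refer to the period after dosing, and no sentence says that baseline is carried forward. A reader might infer that the plan deliberately carries baseline forward. The documents do not say that; it is the result of the literal rule combined with the schedule, and only when a final value is missing. The postdose reading is not in the text either. The pharmacodynamic and efficacy set definitions immediately before the rule say postdose, and the rule itself does not.

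**Missing values should be rare.** This stands. Protocol 3.7.1.1.1 keeps subjects in hospital through the completion or withdrawal assessment, and protocol 3.10 defines completers as those who have the completion assessment. Apart from a lost or uncollected sample, a missing panel needs a discontinued subject without a withdrawal assessment, which protocol 3.8.3.1 encourages.

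**The summaries are descriptive and partly checkable.** This also stands. SAP 6.1 and 6.2 set no primary or secondary outcome. By-visit rows are not imputed, so Day 6 shows observed values for subjects treated for the full five days, although SAP 3.4 leaves discontinuation values out of those rows. Individual values are listed. A reader might infer that the tolerability findings or response rates are biased. The documents do not support that: adverse event tables, any-postdose liver counts and sodium-event counts do not use this rule, and the rates behave as shown in Step 4.

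**Leaving values missing is itself selective.** This is correct, and it is counted as a cost of the fix.

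**Conclusion.** The concern holds as a minor, conditional defect. As written, the rule lets a pre-treatment value be reported as an end-of-treatment value. For central laboratory tests other than sodium and potassium, and for biomarkers, that value is normally the baseline, so the subject shows exactly zero change and, for laboratory tests, no shift. For the cardiothoracic ratio, a screening or predose Day 1 film enters a confidence interval as if it were an end-of-treatment film.

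The size depends on m, which the documents do not give and which may be 0. The range of 0 to 4 is an assumption, as are the mean and SD in the cardiothoracic illustration. The comparison with observed-only results also assumes that subjects with missing values resemble those observed.

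**What to change.** In SAP 5.4, state that:

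1. the final time point is imputed only from values of the same variable obtained after the first dose and no later than the day after the final dose; otherwise it stays missing, and the numbers imputed and missing are reported for each variable;
2. in the NYHA and pulmonary congestion rates, subjects without a postdose value stay in the denominator as not improved.

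The second statement keeps those rates where they are now. Without it, dropping 2 or 4 subjects would raise an assumed 24/40 (60.0%) to 24/38 (63.2%) or 24/36 (66.7%).

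The cost is two sentences and no new data. The number of subjects at the final time point becomes slightly smaller for laboratory tests, biomarkers and cardiothoracic ratio. Those left out are likely to be mainly discontinued subjects, possibly because of adverse events, so the observed-only summary may also look benign. The number missing and the reason for discontinuation should therefore be shown beside each affected summary.

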## **6 Primary and Secondary Outcome Variables:**

### **6.1 Primary Outcome Variables**

Primary outcome variables are not set.

### **6.2 Secondary Outcome Variables**

Secondary outcome variables are not set.

### **6.3 Safety Outcome Variables**

Adverse events, clinical laboratory tests, physical examination, vital signs (blood pressure, pulse rate, and body temperature), and 12-lead electrocardiogram (ECG)

### **6.4 Pharmacodynamic Outcome Variables**

Urine volume, fluid intake, fluid balance, serum sodium concentration, serum potassium concentration, serum osmolality, urine sodium excretion, urine potassium excretion, urine osmolality, and biomarkers (plasma concentrations of AVP and brain natriuretic peptide

[BNP], plasma renin activity, and serum concentrations of N-terminal pro BNP [NTproBNP] and troponin I)

### 6.5 Efficacy Outcome Variables

- Body weight
- Congestive symptoms

Lower limb edema, jugular venous distension, hepatomegaly, pulmonary rales, cardiac third sound, cardiothoracic ratio, and pulmonary congestion

- Dyspnea

Respiratory rate, paroxysmal nocturnal dyspnea, orthopnea, and subject-assessed dyspnea

- New York Heart Association (NYHA) classification

## 7 Disposition and Demographic Analysis

### 7.1 Subject Disposition

For subjects from whom informed consent was obtained (screened subjects), the number of subjects and subjects administered IMP and the numbers and percentages of completed subjects after IMP administration, and discontinued subjects after IMP administration (the denominator indicates the number of subjects administered IMP) will be summarized. For discontinued subjects after IMP administration, the number and percentage of subjects by reason for discontinuation will be summarized. Of the completed subjects after IMP administration, the number and percentage of those who completed treatment in less than a 5-day treatment period (as in [Section 3.2.3](#) in the protocol) will be summarized by reason.

For subjects administered IMP, the number and percentage of subjects included in each statistical analysis set will be summarized.

### 7.2 Demographic and Baseline Characteristics

For the safety analysis set and efficacy analysis set, distributions (number of subjects, %) or descriptive statistics (number of subjects, mean, standard deviation, minimum, median, and maximum) will be calculated according to [Table 7.2-1](#)

**Table 7.2-1 Demographic and Other Baseline Characteristics**

Variable	Time point	Method	Level
Age	Informed consent acquisition	Descriptive statistics	-
		Distribution	20-29, 30-39,

**Table 7.2-1 Demographic and Other Baseline Characteristics**

Variable	Time point	Method	Level
			40-49, 50-59, 60-69, 70-79, 80-85
			<65, ≥65
Sex	-	Distribution	Female, Male, Undifferentiated
Height (cm)	Screening	Descriptive statistics	-
Body weight (kg)	Screening	Descriptive statistics	-
BMI (kg/m  )	Screening	Descriptive statistics	-
Country	-	Distribution	JAPAN
Race	-	Distribution	Asian
Ethnicity	-	Distribution	Not Hispanic or Latino
Primary illness (multiple selection)	Screening	Distribution	Yes, No
• Ischemic heart disease			
• Cardiomyopathy			
• Valvular disease			
• Hypertensive heart disease			
• Arrhythmia			
Type of heart failure	Screening	Distribution	Right Heart Failure, Left Heart Failure, Bi-ventricular Failure, Unspecified
Presence of arrhythmia			Yes, No
Use of Pacemaker	Screening	Distribution	Yes, No
Use of ICD	Screening	Distribution	Yes, No
Complication (multiple selection)	Screening	Distribution	Yes, No
• Hypertension			
• Angina pectoris			
• Diabetes mellitus	Screening	Distribution	
• Renal impairment			
Presence of complication			Yes, No
Presence of medical history	Screening	Distribution	Yes, No
Reason why oral intake was judged difficult or impossible (multiple selection)	Screening	Distribution	Ongoing NPPV therapy, Risk of aspiration, Reduced swallowing function, Other

### 7.3 Baseline Disease Evaluation

For the safety analysis set and efficacy analysis set, each variable at baseline will be calculated.

Table 7.3-1 Baseline Pathologic Evaluation		
Variable	Method	Level
Cardiothoracic ratio (%)	Descriptive statistics	-
NYHA classification	Distribution	Class I, Class II, Class III, Class IV
Severity of lower limb edema	Distribution	None, Mild, Moderate, Severe
Pulmonary congestion	Distribution	None, Mild, Moderate, Severe
Presence of jugular venous distension	Distribution	Yes, No
Jugular venous distension (cm)	Descriptive statistics	-
Presence of jugular venous distension (value at baseline)	Distribution	Yes, No
Jugular venous distension (cm) (subjects with baseline value)	Descriptive statistics	-
Presence of hepatomegaly	Distribution	Yes, No
Hepatomegaly (cm)	Descriptive statistics	-
Presence of hepatomegaly (value at baseline)	Distribution	Yes, No
Hepatomegaly (cm) (subjects with baseline value)	Descriptive statistics	-
Pulmonary rales	Distribution	Yes, No
Third cardiac sound	Distribution	Yes, No
Respiratory rate (breaths/min)	Descriptive statistics	-
Orthopnea	Distribution	Present, Absent
Paroxysmal nocturnal dyspnea	Distribution	Present, Absent
Subject-assessed dyspnea (presence of symptoms)	Distribution	Present, Absent
Daily urine volume	Distribution	<1500 mL, ≥1500 mL
Creatinine	Distribution	<2 mg/dL, ≥2 mg/dL
Plasma AVP concentration	Distribution	≤3.1 pg/mL, >3.1 pg/mL

Table 7.3-1 Baseline Pathologic Evaluation		
Variable	Method	Level
Albumin	Distribution	<3 g/dL, ≥3 g/dL

#### **7.4 Treatment Compliance**

Treatment compliance will be summarized for the safety analysis set and efficacy analysis set. Distributions for presence or absence of discontinuation during IMP (injection) administration will be calculated. Distributions for presence or absence of days of incomplete IMP (injection) administration as well as days on which the duration from start to end of IMP administration is outside the allowable range (55 to 70 minutes) will also be calculated.

#### **7.5 Prior and Concomitant Medications**

No prior and concomitant medications analysis will be performed in this trial.

#### **7.6 Protocol Deviations**

For subjects administered IMP, distributions for presence or absence of deviations in each CRF classification (Dosing, Inclusion/Exclusion Criteria, Met Withdrawal Criteria But Was Not Withdrawn, Prohibited Concomitant Medications) will be calculated. Distributions of subjects with at least one deviation will also be calculated.

### **8 Efficacy Analysis**

The following analyses will be conducted on the efficacy dataset. The same analyses will also be conducted for subjects categorized by the presence or absence of dose escalation (ie, subjects with dose increased to 16 mg and subjects with dose maintained at 8 mg without dose escalation) based on the dose escalation criteria.

#### **8.1 Primary Efficacy Endpoint**

Primary efficacy endpoint are not set.

#### **8.2 Key Secondary Efficacy Endpoint**

Key secondary endpoint are not set.

## 8.3 Efficacy Analyses

### 8.3.1 Body Weight

Descriptive statistics and two-sided 95% confidence intervals (based on t-distribution) will be calculated for measured values and changes from baseline at the time of final IMP administration, and descriptive statistics will be calculated for the percent changes. At each time point, descriptive statistics will be calculated.

### 8.3.2 Congestive Symptoms

#### 8.3.2.1 Lower Limb Edema and Pulmonary Congestion

The number, and proportion with the two-sided 95% confidence intervals (exact) will be calculated for the improvement rate and the resolution rate at the time of final IMP administration. The improvement rate is defined as the proportion of subjects in whom a symptom is present at baseline and then markedly improves or improves after IMP administration (for the improvement category, see [Table 8.3.2.1-1](#)). The resolution rate is defined as the proportion of subjects in whom a symptom is present at baseline and then resolves after IMP administration.

Shift tables for the severity of the symptoms will be prepared at each on-treatment time point and at the time of final IMP administration compared with baseline.

Table 8.3.2.1-1 Improvement Category of Lower Limb Edema and Pulmonary Congestion		
	Improvement category	Assessment criteria
1	Markedly improved	The symptom resolved or improved by $\geq 2$ categories.
2	Improved	The symptom improved by one category. (Symptom resolution will be categorized as “markedly improved.”)
3	Unchanged	The symptom remained unchanged or was absent throughout the trial period.
4	Deteriorated	The symptom worsened by $\geq 1$ category.

